### **6.2.3.12 Phase 2 Assessments at Week 49 (Day 337)**

The following procedures will be performed at the visit for Week 49 (Day 337±3):

- Hematology, chemistry with LDH, and dipstick urinalysis
- Cystoscopy/Cytology and, if indicated, a repeat biopsy – per SOC to evaluate for recurrent disease. *Note: Patients with evidence of disease may continue on treatment if judged by the investigator to be in the patient's best interest. Patients who discontinue study treatment will continue in long-term follow-up. If biopsy was performed, provide at least 4, non-stained, 10 micron sections for TCR sequencing and analysis of infiltrating T-cells. If slides or curls or fresh frozen specimens are not available, FFPE tissue (≥50 microns) is also acceptable.*
- Record adverse events
- Record concomitant medications

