### 6.3 Long-term Follow-up Visits

All patients will be followed for the procedures listed below every 3 months from the date of the previous visit for 2 years then every 6 months from the date of the previous visit for a year or until study termination, whichever occurs first:

- Survival
- New anticancer treatments initiated after disease recurrence
- TURBT or fulguration procedures
- Cystectomy

In addition patients who have completed all study treatments or have discontinued study product dosing due to reason other than disease recurrence/progression will have the following procedures performed at each long-term follow-up visit:

- Cystoscopy/Cytology; biopsy if area suspicious for disease recurrence is identified at discretion of investigator (*Note: patients who have a biopsy performed will provide at least 4, non-stained, 10 micron sections for TCR sequencing and analysis of infiltrating T-cells.*) *If slides are not available, FFPE tissue (≥50 microns) is also acceptable.*

If a patient has recurrent/progressive disease and discontinues study treatment, the above disease assessment procedures will be discontinued, and subsequent long-term follow-up visits may be conducted via phone visit.

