#### **12.5.1 Primary Efficacy Analysis**

##### **12.5.1.11-year Disease-Free Survival (1-yr DFS)**

One-year disease-free survival will be defined as the proportion of patients who are free from recurrent disease, progressive disease, and alive one year after the date of randomization/treatment assignment (Arm 4).

For the primary efficacy evaluation, disease-free survival at one year between the experimental groups and the control will be presented as the absolute difference in proportions, as well as the OR, with the associated 95% CI.

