2.1 Study Objectives

Primary Objective

- **Phase 1:** To characterize the safety and tolerability of monotherapy vaccination with HS-410 in patients with non-muscle invasive bladder cancer.
- **Phase 2:**
 - Arms 1, 2, and 3: To evaluate 1-year disease-free survival in patients with non-muscle invasive bladder cancer treated with BCG in combination with blinded study product (one of two doses of vesigenurtacel-L or placebo).
 - Arm 4: To evaluate 1-year disease-free survival in patients with non-muscle invasive bladder cancer treated with high dose vesigenurtacel-L monotherapy.

Secondary Objectives

Both Phases:

- To evaluate the proportion of patients with recurrence at 3, 6, 12, 18, and 24 months
- To evaluate the proportion of patients with progressive disease at 3, 6, 12, 18, and 24 months
- To evaluate overall disease-free survival
- To evaluate overall survival (OS)
- To evaluate the proportion of patients undergoing post-treatment TURBT or fulguration by 12 and 24 months
- To evaluate the proportion of patients undergoing cystectomy by 12 and 24 months
- To evaluate the proportion of patients with immunologic response of PBMCs via intracellular cytokine staining (ICS) by flow cytometry and/or ELISPOT on CD8+ cells following vesigenurtacel-L vaccination

Phase 2 only:

- To evaluate the safety of the combination of vesigenurtacel-L and BCG
- To evaluate the safety of high dose vesigenurtacel-L monotherapy

Primary Endpoint

- **Phase 1:** Safety and tolerability of monotherapy vaccination with HS-410 in patients with non-muscle invasive bladder cancer.
- **Phase 2:** 1-year disease-free survival in patients with non-muscle invasive bladder cancer treated with BCG in combination with one of two doses of HS-410 or placebo, or with high dose HS-410 without BCG. The 1-year disease-free survival rate is defined as the proportion of patients who are alive and free from recurrence and progression at 12 months following randomization.

Secondary efficacy endpoints:

Both Phases:

- Proportion of patients with recurrence at 3, 6, 12, 18, and 24 months from randomization, estimated based on Kaplan-Meier curves. Recurrence is defined as disease that has recurred to the same extent of disease (ie same stage / severity) or to a lower stage/severity of disease compared to screening.

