7.1 Primary Efficacy Analysis

The primary efficacy parameter is 1 year DFS and will be conducted on the ITT population. It will be calculated as the proportion of patients in the experimental groups and the control who remain disease free at 1 year. Hypothesis testing on the primary endpoint will be done one-sided at a level of significance of $\alpha = 0.10$ using Fisher's exact test. The absolute difference in proportions, as well as the odds ratio, with the associated 95% confidence intervals will also be presented.

The following rules will be used to determine whether a patient is disease free at 1 year or not

- If a patient has a recurrence before day 394 (ie day 366+28 days) or has dropped out of the study before day 394, then the patient is considered to be not disease free at 1 year.
- If a patient is shown to be free from disease on day 366 +/- 28 days, then the patient is considered to be disease free at 1 year.
- If a patient has no recurrence before day 338 (ie day 366-28 days) and after day 394 (day 366+28 days), then the patient is considered to be disease free at 1 year.

If the analysis of the primary endpoint does not suggest any dose response effect between the two vaccine arms, an exploratory analysis will be conducted where the two vaccine arms will be pooled and compared to the control arm for the primary endpoint (proportion of patients alive and disease-free at one year). The outcome will be presented as OR with 95% CI relative to the control group.

In an additional exploratory analysis, the proportion of patients whose disease has recurred to a lower stage than at screening and the proportion of patients whose disease has recurred to the same extent (or greater) as at screening will be compared between the experimental and control groups and presented as an OR with 95% CI.

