7.2 Secondary Efficacy Analyses

For time-to-event endpoints (e.g. DFS, OS), Kaplan-Meier / product limit method will be used to estimate the survival distributions over time, and to estimate median time to event. Where appropriate, inference for time-to-event endpoints will be assessed using the Log-rank test statistic, and the treatment effect will be estimated using Cox proportional hazards model. The assumption of proportional hazards will be assessed graphically.

The following will be analysed using Kaplan-Meier time-to-event methodology:

- Time To Recurrence, defined as the time from randomization to recurrence.
 - Recurrence is defined as disease that has recurred to the same extent of disease (ie same stage / severity) or to a lower stage/severity of disease compared to screening.
 - If recurrence has not occurred in a patient, the date of last disease assessment will be used as the timepoint for censoring.
 - The analysis will be repeated in an exploratory manner where recurrence is defined as only those recurrences to the same extent of disease (or greater) as screening.

- Time To Progression, defined as the time from randomization to progression.
 - Progression is defined as an increase in T stage from CIS or Ta (at screening) to T1 (lamina propria invasion), development of T2 or greater or lymph node (N+) disease or distant metastasis (M1), or an increase in grade from low to high per the IBCG recommendations..
 - If progression has not occurred in a patient, the date of last disease assessment will be used as the timepoint for censoring.

- Disease-Free Survival, defined as the time from randomization to recurrence or progression.
 - If a patient has recurred or progressed, then the first date the recurrence or progression has occurred will be used as the timepoint for the event.
 - If a patient has neither recurred nor progressed, then the date of last disease assessment will be used as the timepoint for censoring.

- Overall Survival, defined as the the time from randomization to death.
 - If a patient is still alive, then the patient will be censored on the date of most recent date known alive.
 - If a patient is lost to follow up, then the patient will be censored on the date last known alive.

- Time to cystectomy, defined as the time from randomization to cystectomy.
 - If a patient has not undergone cystectomy, the patient will be censored on the date of last disease assessment.

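### The SAP 7.1 scoring rules do not implement the primary endpoint: progression and death are not named as failures, the rules overlap without a stated order, and persistent CIS is unreconciled

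*SAP*

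**What the plan says.** **Endpoint.** SAP 2.1 defines one-year disease-free survival as "the proportion of patients who are alive and free from recurrence and progression at 12 months following randomization". Protocol 12.5.1.1 has the same components: "free from recurrent disease, progressive disease, and alive one year after the date of randomization/treatment assignment (Arm 4").

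**Scoring rules, SAP 7.1.**
- Rule 1, not disease-free: "If a patient has a recurrence before day 394 (ie day 366+28 days) or has dropped out of the study before day 394".
- Rule 2, disease-free: "If a patient is shown to be free from disease on day 366 +/- 28 days".
- Rule 3, disease-free: "If a patient has no recurrence before day 338 (ie day 366-28 days) and after day 394 (day 366+28 days").

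No order of precedence is given.

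**Recurrence.** SAP 7.2 states: "Recurrence is defined as disease that has recurred to the same extent of disease (ie same stage / severity) or to a lower stage/severity" relative to screening; SAP 2.1 has the same definition. Both sections define progression separately.

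**Follow-up after an event.** Progression ends study treatment (protocol 7.2.1), but follow-up for endpoints continues unless consent to it is withdrawn (7.2.2). Only the cystoscopies stop: "If a patient has recurrent/progressive disease and discontinues study treatment, the above disease assessment procedures will be discontinued" (6.3).

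**Persistent CIS.** Protocol 10.1 makes CIS still present by six months a category of its own. Protocol 12.5.2.4 gives it an overall DFS of zero, and protocol 3.1 says disease-free status in the analysis follows section 10.1. Protocol 12.5.1.1 and SAP 2.1 and 7.1 do not mention it.

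**The concern.** The rules are what a programmer will code, and they test for something narrower than the endpoint. Progression and death, two of its three failure components, are not named in any rule. Followed to the letter, the rules score some failures as disease-free, give two answers for some patients and none for others. Those choices would then be made in programming rather than in the plan. This is the endpoint to which SAP 5.5 confines p-values, with 25 patients randomized per arm, so a few such decisions carry weight.

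**Working it through.** **1. Rules applied literally to test patients.** Rule 3 is taken as worded: no recurrence before day 338 and none after day 394.

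| Patient | Rule 1 (fail) | Rule 2 (disease-free) | Rule 3 (disease-free) | Outcome |
|---|---|---|---|---|
| Progression day 200, stays in follow-up | no | no | yes | disease-free |
| Death day 200, not coded as drop-out | no | no | yes | disease-free |
| CIS at 3 and 6 months, not coded as recurrence, no clear result in window | no | no | yes | disease-free |
| Clear day 345, drop-out day 380 | yes | yes | yes | contradictory |
| Recurrence day 360 | yes | no | yes | contradictory |
| Clear day 337, first recurrence day 477 | no | no | no | no rule |
| Clear day 340, first recurrence day 477 | no | yes | no | disease-free |

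If rule 3 is instead taken to need a clear assessment after day 394, the progressed patient has none, because cystoscopies have stopped. That patient then has no classification. Neither reading returns a failure.

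**2. Visit timing.** The Week 49 cystoscopy is "performed at the visit for Week 49 (Day 337±3"), so study days 334 to 340. Rule 2's window is 366 − 28 = 338 to 366 + 28 = 394. Visits on days 334–337 miss it and visits on days 338–340 fall inside. Study days count from first dose, while the endpoint runs from randomization, and SAP 3.5 allows up to 3 days between them. Counted from randomization the visit range is therefore 334 to 340 + 3 = 343. The Week 56 visit lists no cystoscopy. The first long-term follow-up visit, about 91 days after Week 56 (day 386), falls near day 477. A shift of a few days therefore decides whether rule 2 or rule 3 applies; the last two table rows differ only in that.

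**3. Persistent CIS.** A patient with CIS at six months that later clears, and who is clear in the window, passes rule 2. The same patient has an overall DFS of zero under protocol 12.5.2.4.

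**4. Time-to-event DFS (secondary).** Death is an event in protocol 12.1 and 12.5.2.4. It is absent from protocol 12.5.2.3, from the overall-DFS line in SAP 2.1 and from SAP 7.2. SAP 7.2 censors anyone without recurrence or progression at the last disease assessment, which includes patients who died.

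**5. The plan's power figure.** Inputs: 60% v 90%, one-sided alpha 0.10 and 80% power (protocol 12.6.2, SAP 4), 23 evaluable per arm (SAP 4), Fisher's exact test (SAP 7.1). Summing the binomial probabilities of all tables with one-sided p ≤ 0.10 gives 80.8%. The stated 80% is reproduced.

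**6. Illustration of size.** Let s be the share of true failures scored disease-free, an assumption because the documents give no such rate. Scored rate = p + s(1 − p). For s = 0.10 in every arm: control 0.60 + 0.10 × 0.40 = 0.64; vaccine 0.90 + 0.10 × 0.10 = 0.91.

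| s, every arm | Scored rates | Difference (points) | Power, 23 per arm | Power, 25 per arm |
|---|---|---|---|---|
| 0 | 60 v 90 | 30 | 80.8% | 84.2% |
| 10% | 64 v 91 | 27 | 75.4% | 79.3% |
| 20% | 68 v 92 | 24 | 69.1% | 73.3% |
| 30% | 72 v 93 | 21 | 62.0% | 66.2% |

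Unequal shares change the direction. With 30% of vaccine failures only, the rates are 60 v 93, a 33-point difference, and power at 23 per arm is 89%. With 30% of control failures only, they are 72 v 90, an 18-point difference.

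One observed table: 15 v 22 disease-free of 25 gives p = 0.025. Re-scoring about 30% of the 10 control and 3 vaccine failures gives 18 v 23 and p = 0.069, still below 0.10.

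**The case against.** The strongest reply is that the intent is plain. SAP 7.1 speaks of patients who remain disease-free, restates the endpoint as being alive and disease-free, and in an exploratory analysis uses recurrence for disease of equal or greater extent. With SAP 2.1 naming all three components, few analysts would knowingly pass a patient who had progressed or died. That stands as evidence of intent. It does not repair the rules: the SAP's stated definition of recurrence excludes progression, and its DFS definition in 7.2 names recurrence and progression separately when both are meant.

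Four stronger readings are tempting and are not supported:

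- *That a patient who recurs early, continues treatment and is clear at one year is left open.* This is largely settled. Protocol 10.1 dates recurrence at the earliest diagnosis whether or not treatment continues, and protocol 3.1 applies that definition to the analysis.
- *That the Week 49 cystoscopy always misses the window.* Day 337 is only the target; part of the allowed range lies inside. How many patients would depend on rule 3 is unknown.
- *That omitting persistent CIS contradicts the stated primary endpoint.* The endpoint definitions do not name it either, and the zero-DFS rule is written for a secondary endpoint. The defect is that the passages are not reconciled.
- *That mis-scoring necessarily costs power.* That follows only if the shares are similar across arms.

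**Conclusion.** The point holds as a defect in the text of SAP 7.1. Progression is not covered by rule 1 as the SAP defines its terms, and death is covered only if read as drop-out. Rule 1 conflicts with rules 2 and 3 with no stated order, and a patient clear just before day 338 whose first recurrence comes after day 394 meets no rule. Whether persistent CIS at six months is a primary-endpoint failure is unresolved between the documents, although protocol 3.1 and 12.5.2.4 imply that it is.

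The size is not known. A fall in power from 81% to 62% is the far end of an illustration that assumes the same 30% share in every arm; it is not a forecast. With unequal shares the bias can run either way, and a single result need not change. The planned 80% power is not itself in error. The effect of censoring deaths in time-to-event DFS cannot be sized from the documents. The case for correction rests on pre-specification of the primary endpoint, so it should be made before the primary analysis is programmed and unblinded.

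**What to change.** In SAP 7.1:

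1. Replace recurrence in rules 1 and 3 with one DFS event set: recurrence, progression or death from any cause, with disease events dated as in protocol 10.1.
2. State that rule 1 takes precedence over rules 2 and 3.
3. State how a patient who is clear in the window but drops out before day 394 is scored.
4. Rewrite rule 3 so that a patient with no in-window assessment is disease-free only if there was no DFS event before day 394 and either a later assessment or a specified pre-window assessment supports it. Say explicitly how a patient clear just before day 338 with a first event after day 394 is scored.

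Across both documents:

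5. Reconcile protocol 10.1, 12.5.1.1 and 12.5.2.4 with SAP 2.1 and 7.1 on persistent CIS at six months, and state whether it is a primary-endpoint failure.
6. Count death as a DFS event in protocol 12.5.2.3, in the overall-DFS line of SAP 2.1 and in SAP 7.2.

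The cost is SAP wording and a protocol clarification. Item 5 deserves care, because it makes the primary endpoint explicit on an event its definition does not now name. Stage at relapse, persistent CIS and survival are already collected, so no new data are needed. The downside is a slightly lower scored disease-free rate.

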### **6.2.3.14 Phase 2 Week 56 (Day 386 ±3) – End of Treatment Visit (4 weeks post last dose)**

The following procedures should be completed approximately four weeks following last dose of study product including patients who discontinue study product dosing prematurely.

- Physical exam (full examination as well as weight and vital signs)
- 12-lead ECG

- Blood and urine collection for immune monitoring
- Hematology, chemistry with LDH, and dipstick urinalysis
- Urine or serum pregnancy test for female patients of childbearing potential
- Autoimmune Labs (ANA, TSH, ESR, and C-reactive protein are required; RF, T3, T4, and thyroid antibodies if clinically indicated)
- Autoimmune Phenomena – Assessment of adult autoimmune system disorders (including: eye exam for dry eyes, lymph node and joint assessment for swelling, and skin exam for vitiligo and rash)
- Record concomitant medications
- Record adverse events

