3.5 Study Variables

In general, the schedules of assessments (SOA) are divided into an induction and maintenance phase.

In the phase 1 component of the study, the induction phase will consist of 6 weekly vaccine doses, a one week drug free period and then followed by 6 more weekly doses. The maintenance phase will then consist of monthly treatments for 3 doses for up to a total of 15 doses, unless the criteria for treatment discontinuation are met.

In the phase 2 component of the study, the induction phase will consist of 6 weekly HS-410 (or placebo) doses in combination with 6 doses of BCG, followed by 6 weeks of HS-410 or placebo monotherapy with a vaccine holiday on Week 13 to allow for disease assessment. This will be followed by a maintenance phase consisting of 3 courses of three once-weekly injections in combination with intravesical maintenance BCG for a total of 21 doses, unless the criteria for treatment discontinuation are met. Additional maintenance therapy will be at the discretion of the treating physician.

Current Schedule of Assessments for each study are contained in the study protocol.

Study Day and Visit Windows

Patients' time on study will be determined in Study Days. Study Day 1 will be defined as the first day of dosing. Positive study days will count forward from Study Day 1. Study Day -1 will be the day before Study Day 1, and all subsequent negative study days will be measured backward from Study Day -1. There will be no Study Day 0.

A value obtained on Study Day 1 before administration of study treatment will be considered the baseline value. If a value is not available on Study Day 1, the last available value collected prior to the first dose of study drug will be used as the baseline value. The study date and corresponding study visit will be captured on each case report form (CRF) from which study day will be calculated.

Study Day will be used in the analysis of safety data and efficacy analysis. The protocol allows a 3-day window between randomization and first dose. All efficacy analyses on time-to-event endpoints will consider the date of randomization as Day 1.

4 Sample Size

Phase 1

Phase 1 is designed to provide some indication of safety and tolerability of the low dose of HS-410 as a monotherapy. A sample size of 10 patients in the monotherapy setting is deemed suitable for an assessment of safety.

Phase 2

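### The Week 49 cystoscopy (Day 337±3) straddles the opening of the SAP's 1-year window (day 338), so for some patients a day of visit timing decides whether any scoring rule applies

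*SAP*

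**What the plan says.** SAP 7.1 gives three rules for the binary primary endpoint.

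- First rule: recurrence or dropout before day 394 means not disease free.
- Second rule: "If a patient is shown to be free from disease on day 366 +/- 28 days", the patient is disease free. The window is therefore days 338 to 394.
- Third rule: "If a patient has no recurrence before day 338 (ie day 366-28 days) and after day 394 (day 366+28 days"), the patient is disease free.

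The SAP gives no order of precedence among them.

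The Phase 2 cystoscopies come from the protocol. Section 6.2.3.12 has the last on-treatment one "performed at the visit for Week 49 (Day 337±3"). The visit in section 6.2.3.14, "Phase 2 Week 56 (Day 386 ±3) – End of Treatment Visit (4 weeks post last dose"), falls inside the SAP window, but neither that section nor the schedule of events (6.2.1) lists cystoscopy or cytology for it. Under section 6.3, follow-up then runs "every 3 months from the date of the previous visit for 2 years".

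The two documents count days from different origins. SAP 3.5 makes the first dosing day Study Day 1 and notes: "The protocol allows a 3-day window between randomization and first dose". The endpoint itself runs from randomization (SAP 2.1, Protocol 12.5.1). SAP 3.5 names randomization as Day 1 for time-to-event endpoints, but does not say so for this binary one.

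**The concern.** The examination that the protocol provides for the 1-year reading sits on the edge of the window that is meant to capture it. Take two patients, both clean at Week 49 and both with recurrence first found after day 394. The one examined on day 338 is disease free under the second rule. The one examined on day 337 misses the second rule, fails the third because of the later recurrence, and is not caught by the first because the recurrence came after day 394. The SAP has no outcome for that patient.

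This is the primary endpoint for the randomized arms and for Arm 4. An unclassified patient would have to be settled by a decision taken once the data exist. With 25 per arm, one patient can matter. As an illustration, under the planned one-sided Fisher test at 0.10, 21 versus 17 disease free gives p = 0.160 and 21 versus 16 gives p = 0.098.

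**Working it through.** **Dates.** Week w starts on day 7(w−1)+1, so Week 49 is 7×48+1 = Day 337 and Week 56 is 7×55+1 = Day 386, as the protocol states. The window is 366−28 = 338 to 366+28 = 394, as the SAP states. Taking 3 months as 91 days, the next cystoscopy is at 337+91 = day 428 if counted from Week 49, or 386+91 = day 477 if counted from the end-of-treatment visit.

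**Allowed Week 49 days against the window, counted from randomization:**

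| Gap, randomization to first dose | Week 49 range | Inside (day 338 or later) | Outside |
|---|---|---|---|
| 0 days | 334–340 | 3 of 7 | 4 of 7 |
| 1 day | 335–341 | 4 of 7 | 3 of 7 |
| 2 days | 336–342 | 5 of 7 | 2 of 7 |
| 3 days | 337–343 | 6 of 7 | 1 of 7 |

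No permitted gap brings in all seven days.

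**Scoring a patient with a negative Week 49 cystoscopy:**

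| What follows | Examined day 337 | Examined day 338 |
|---|---|---|
| Next cystoscopy (after day 394) negative | disease free, third rule | disease free, second rule |
| Recurrence first found at next cystoscopy (after day 394) | no rule applies | disease free, second rule |
| Dropout before day 394 | not disease free, first rule | first and second rules conflict |
| Dropout after day 394, no further cystoscopy | third rule has no later examination behind it | disease free, second rule |

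A positive Week 49 cystoscopy fails under the first rule on either day.

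**Size of the second row.** Assumptions: constant hazard matching 60% (control) and 90% (vaccine) at 1 year, detection at cystoscopy only, and visits spread evenly over the seven allowed days.

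- Daily hazard: −ln(0.6)/365.25 = 0.001399 for control; −ln(0.9)/365.25 = 0.000288 for vaccine.
- Probability that a patient clean at day 337 recurs by day 428 (91 days) or day 477 (140 days), 1−exp(−hazard×days): control 0.120 or 0.178; vaccine 0.026 or 0.040.
- Clean patients per arm, taken as the 1-year figure: 25×0.6 = 15 and 25×0.9 = 22.5.
- With 4/7 outside: control 15×0.120×4/7 = 1.0 to 15×0.178×4/7 = 1.5; vaccine 22.5×0.026×4/7 = 0.3 to 22.5×0.040×4/7 = 0.5.
- With 1/7 outside: control 0.26 to 0.38; vaccine 0.08 to 0.13.

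**Bounding case.** Set the hazards to reach 60% and 90% at day 366. If every visit is on day 338 or later, expected disease-free rates are about 62.5% and 90.8%, a difference of 28 points. If every visit is on day 337 or earlier and the unclassified patients are counted as failures, the rates are about 55.0% and 88.4% (33 points) with the next cystoscopy at day 428, or 51.4% and 87.2% (36 points) at day 477.

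**Falling hazard.** Protocol 1.1 gives recurrence-free rates of 62% at one year and 38% at five for intermediate risk, and 39% and 20% for high risk.

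- Intermediate risk: the mean annual hazard after year 1 is ln(0.62/0.38)/4 = 0.122, against −ln(0.62) = 0.478 in year 1, a ratio of 0.26.
- High risk: ln(0.39/0.20)/4 = 0.167 against −ln(0.39) = 0.942, a ratio of 0.18.
- Applying these ratios to the control hazard after day 366, 5% to 8% of clean controls recur by day 428 to 477. With 4/7 outside that is about 0.5 to 0.7 patients.

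**The case against.** The strongest reply is that timing seldom alters the score. Patients positive at Week 49 fail either way, and patients clean at both Week 49 and the next cystoscopy are disease free either way; the third rule looks like the SAP's own provision for patients with no examination in the window. That stands, and it confines the problem to late-found recurrences and some dropouts.

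Four further points also stand. Patients who stop dosing early without recurrence move to the long-term schedule, so some of their cystoscopies may fall in the window. The Kaplan-Meier estimate of disease-free survival at 12 months in SAP 7.2 uses no such window. A day-477 examination would leave 20 weeks between cystoscopies, whereas Protocol 10.1 asks for one every 3 months, so the upper end of the range is the less likely one. And the counts rest on assumed hazards, with the declining rates in Protocol 1.1 pointing to smaller ones, although those rates are not specific to this BCG regimen.

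Three stronger readings are tempting, and the documents do not support them.

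- A reader might infer that a patient examined exactly on schedule can never meet the second rule. That is so only when first dose falls on the randomization day. With a gap of 1 to 3 days the on-target visit is day 338 to 340, inside the window.
- A reader might infer that the endpoint becomes a 14- to 16-month outcome. That requires counting the unclassified patients as failures, and SAP 7.1 does not say to do so.
- A reader might infer a bias towards the vaccine. Inflation of the difference needs both that failure convention and the planned 60% versus 90% to be true. With equal hazards the expected effect is the same in each arm, so no false-positive bias is shown.

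None of this supplies the missing rule.

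**Conclusion.** The mismatch is real and should be fixed. For patients on the full Phase 2 schedule, Week 49 is the only planned cystoscopy that can fall in the 1-year window, and between 1 and 4 of its 7 allowed days fall before the window opens. A patient clean on one of those days whose recurrence is first found after day 394 has no defined primary outcome, whereas the same patient seen from day 338 is disease free. This takes the third rule as failing on any recurrence found after day 394; its wording is loose, and it does not say whether a negative later examination is required.

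Over the full range of gaps, about 0.3 to 1.5 control patients and 0.1 to 0.5 per vaccine arm of 25 are affected, under the constant-hazard and even-spread assumptions. Dropouts are extra and were not counted. No figure is offered for Arm 4, for which the plan assumes no rate. The expected numbers are small and the SAP describes the trial as exploratory, so this is a repair that should be made rather than a defect that invalidates the endpoint.

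**What to change.** Change the wording of SAP 7.1 before database lock.

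1. State that days for the primary endpoint count from randomization (treatment assignment for Arm 4).
2. Open the window at day 334 or earlier, so that it holds every allowed Week 49 visit even with no gap before first dose, and change the day-338 limit in the third rule to match.
3. Give an order of precedence. Recurrence, progression or death up to day 394 is not disease free and overrides a clean Week 49 examination. Otherwise a patient with no evidence of disease in the window is disease free, whatever is found after day 394. The third rule applies only when there is no examination in the window.
4. Say whether dropout before day 394 after a clean in-window examination falls under the first or the second rule.

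The precedence in item 3 is needed. Widening the window alone could let a patient who is clean at Week 49 and recurs or dies before day 394 be scored as disease free, against the first rule and the endpoint definitions in Protocol 12.5.1 and SAP 2.1.

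The cost is SAP text only: no visit, procedure or treatment changes. The drawback, which the SAP should state openly, is that for most patients the 1-year endpoint is read at about 48 weeks.
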